**Table 10 Criteria for PCS laboratory values**

Laboratory data	Very Low	Very High
Laboratory hematology		
Hemoglobin [g/L]	<80	
Platelets [ $10^9/L$ ]	<50	
Laboratory clinical chemistry		
ALT		>5 x ULN and >= 2 x baseline
AST		>5 x ULN and >= 2 x baseline
Creatinine [ $\mu\text{mol}/\text{L}$ ]		>132.605
Creatinine clearance [ $\text{mL}/\text{min}$ ]***	<50	

\*\*\* estimated by Cockcroft-Gault-Formula (see above)

Additionally, for hemoglobin and creatinine clearance, the number and percentage of subjects with a maximum Common Terminology Criteria for Adverse Events (CTCAE) Grade of 0, 1, 2, 3, or 4 (see definitions in Table 12) at any post-baseline visit (regardless of the baseline value) through the end of treatment (i.e., Final Treatment Value) will be summarized. For the liver function tests (LFTs) of ALT and AST, the number and percentage of subjects in with a maximum CTCAE Grade of 0, 1, 2, 3, or 4 (see definitions in Table 12) at any post-nadir visit through the end of treatment (i.e., Final Treatment Value) will be summarized. Note, for these analyses, the nadir is used for reference (including baseline).

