**Table 4 - Analysis Time Windows**

Phase	Time point	Time Window
Pre-Treatment	Baseline	Last value prior to start of study treatment (i.e. $\leq$ study day 1)
Treatment Weeks	4 (day 29)	Study day during treatment period (Study day 1 = first treatment day) 15 - 42
	8 (day 57)	43 - 70
	12 (day 85)	71 - 98
	16 (day 113)	99 - 126
EoT	Actual EoT	Study day of last dose (28 days prior to EoT - 14 days post EoT)
Post Treatment	4 weeks (28 days post EoT)	8 – 56 post EoT
	12 weeks (84 days post EoT)	57 – 126 post EoT
	24 weeks (168 days post EoT)	127 – 252 post EoT
	48 weeks (336 days post EoT)	253 – 420 post EoT

Mean changes from baseline to each post-baseline visit will be summarized descriptively.

Laboratory data values collected during the treatment period will be categorized as low, normal, or high based on reference ranges used in this study. The number and percent of patients who experience post-baseline shifts during treatment in clinical laboratory values

Confidential Information

No use or disclose outside AbbVie is permitted without prior written authorization from AbbVie  
Version 3.0. (22. Apr 2015) – Germany V3.0 (17. November 2016)

Page 41 of 63

from low/normal to high and high/normal to low based on the reference range will be summarized.

Additional details of the analyses of clinical laboratory data will be specified in the SAP.

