#### **4.2.6.4 Co-morbidities and co-infections**

A summary table will present the absolute and relative frequencies of HCV co-infections, CHC related comorbidities and other co-morbidities, in more detail:

- HCV Co-infections
  - Human immunodeficiency virus (HIV)
  - Hepatitis B virus (HBV)
  - Tuberculosis
  - Schistosomiasis
- Liver and/ or CHC related co-morbidities
  - Liver transplantation
  - Hepatocellular carcinoma
  - Steatosis (non-alcoholic)
  - Alcoholic liver disease
  - Primary biliary cirrhosis
  - Auto-immune hepatitis

- Wilson disease
- Cryoglobulinemia
- Porphyria cutanea tarda (PCT)
- Auto-immune skin disease
- Other co-morbidities
  - Kidney transplant
  - Chronic kidney disease (Mild, Moderate, Severe, Currently on dialysis, Currently not on dialysis)
  - Psychiatric disorders (Depression, Bipolar disorder, Schizophrenia, Personality disorder)
  - Diabetes mellitus (Type 1, Type 2)
  - Insulin resistance
  - Metabolic syndrome
  - Lipid disorder
  - Hyperthyroidism
  - Hypothyroidism
  - Cardiovascular disease (Myocardial infarction, Angina pectoris, Hypertension, Stroke)
  - Immunologically mediated disease
  - Hemophilia
  - Thalassemia
  - Sickle cell anemia
  - V. Willebrand disease
  - Psychoactive substance dependency (Active injection drug use, Inhalate cocaine, Marihuana/ cannabis, Opiate substitution)
  - Other

The patient's alcohol consumption will be displayed in a further table, i.e.:

- Alcohol use (None, Yes – occasional, Yes – regular, Ex-drinker [6 units/drinks per day, none in the last 3 months])
- Average number of units/drinks per week (if regular alcohol use is reported)

One unit/drink is defined as 10 milliliters (or approximately 8 grams) of pure alcohol and equals: 200 ml of beer or 100 ml of wine or 20 ml of hard liquor.

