#### **4.2.8.4 *Laboratory Data***

All reported clinical laboratory test results will be assigned to one of the time points using the time windows specified in the Table 5. All will be performed for the SP by treatment regimen and cirrhosis status.

Changes from baseline to each post-baseline visit will be summarized descriptively (N, mean, SD, median, minimum, maximum). A summary table will show laboratory hematology. In another table information about clinical chemistry will be summarized.

In a further table CD4 and HIV-RNA are displayed for patients with HIV only by visit.

Instead of the shift tables mentioned in the study protocol, the number and percentage of subjects with post-baseline values until EoT meeting the specified criteria for Potentially Clinically Significant (PCS) laboratory values (defined in Table 11) will be summarized. A post-baseline value must be more extreme than the baseline value to be considered a PCS finding.

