**Table 11 Definition of CTCAE Grades 0-4**

Laboratory data	Grade 0	Grade 1	Grade 2	Grade 3	Grade 4
ALT	$\leq\text{ULN}$	$\text{>ULN} - 3 \times \text{ULN}$	$> 3 - 5 \times \text{ULN}$	$> 5 - 20 \times \text{ULN}$	$> 20 \times \text{ULN}$
AST	$\leq\text{ULN}$	$\text{>ULN} - 3 \times \text{ULN}$	$> 3 - 5 \times \text{ULN}$	$> 5 - 20 \times \text{ULN}$	$> 20 \times \text{ULN}$
Hemoglobin Decreased [g/L]	$\geq 130$	$< 130 - 100$	$< 100 - 80$	$< 80 - 65$	$< 65$
Creatinine Clearance [ $\text{mL}/\text{min}$ ]	$\geq 75$	$< 75 - 60$	$< 60 - 30$	$< 30 - 15$	$< 15$

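### The worst-grade summary for haemoglobin and creatinine clearance ignores the baseline grade, so it cannot separate pre-existing abnormality from worsening on treatment, and no other described output fully fills that gap

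*SAP*

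**What the plan says.** Protocol 9.7.4 planned patient-level shift counts against the reference range: "The number and percent of patients who experience post-baseline shifts during treatment in clinical laboratory values" from low or normal to high, and from high or normal to low.

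SAP 4.2.8.4 changes this. "Instead of the shift tables mentioned in the study protocol", it summarises PCS laboratory values, with the condition: "A post-baseline value must be more extreme than the baseline value to be considered a PCS finding". The PCS criteria (printed as Table 10) include haemoglobin below 80 g/L, creatinine clearance below 50 mL/min and creatinine above 132.605 µmol/L.

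Below that table the SAP adds a second summary of the maximum CTCAE grade from 0 to 4. For haemoglobin and creatinine clearance it is taken "at any post-baseline visit (regardless of the baseline value) through the end of treatment". For ALT and AST, in the same paragraph, only post-nadir visits count: "Note, for these analyses, the nadir is used for reference (including baseline".

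The grade limits are in the table printed as Table 11 (the SAP text cites these tables one number higher). The output, twlv_, is titled Worst Laboratory Values and is run in the safety population by treatment regimen and cirrhosis status. The same section also states: "Changes from baseline to each post-baseline visit will be summarized descriptively".

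**The concern.** A count of maximum grade that takes no account of the starting value mixes two quantities: how many patients entered with a low value, and how many became worse. If nobody's value changes, the table reproduces the baseline prevalence of each grade.

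The population makes this more than a formality. The safety population (SAP 4.2.1) has no exclusion for anaemia or renal impairment. SAP 4.2.6.4 lists chronic kidney disease with dialysis status among the co-morbidities, and SAP 4.2.6.1 provides an age category of 85 years and over. Table 11 places every patient below 130 g/L, man or woman, in haemoglobin Grade 1 or higher.

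Tolerability is a stated objective. Protocol 7.1 attributes many laboratory abnormalities to ribavirin and mentions ribavirin-induced haemolysis, and the output is laid out in columns with and without ribavirin. Readers will look to a table of graded haemoglobin for worsening on treatment, which this rule cannot show.

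**Working it through.** The documents give no expected rate for this table, so there is no plan figure to reproduce. The check has three steps.

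**1. Patients with no change on treatment.** Formula (SAP 4.2.6.5): clearance = (140 − age) × weight × constant / creatinine in µmol/L, with constant 1.23 for men and 1.04 for women. Limits (Table 11):

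- Haemoglobin, g/L: Grade 0 at 130 or above; Grade 1 from 100 to below 130; Grade 2 from 80 to below 100; Grade 3 from 65 to below 80; Grade 4 below 65.
- Clearance, mL/min: Grade 0 at 75 or above; Grade 1 from 60 to below 75; Grade 2 from 30 to below 60; Grade 3 from 15 to below 30; Grade 4 below 15.

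The patient values are illustrative assumptions.

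| Stable patient | Calculation | Counted as |
|---|---|---|
| Haemoglobin 125 g/L | – | Grade 1 |
| Haemoglobin 98 g/L | – | Grade 2 |
| Man, 75 y, 70 kg, creatinine 88 | 65 × 70 × 1.23 / 88 = 63.6 | Grade 1 |
| Woman, 70 y, 60 kg, creatinine 75 | 70 × 60 × 1.04 / 75 = 58.2 | Grade 2 |
| Man, 60 y, 70 kg, creatinine 400 to 800 (assumed dialysis range) | 80 × 70 × 1.23 / 400 = 17.2; / 800 = 8.6 | Grade 3 to 4 |
| Woman, 60 y, 60 kg, same range | 80 × 60 × 1.04 / 400 = 12.5; / 800 = 6.2 | Grade 4 |

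A patient who falls from 140 to 105 g/L is also Grade 1, so the table cannot tell that patient from the one who stayed at 125.

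**2. Whether another output supplies the missing count.**

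- *PCS table.* It is conditioned on baseline, but with one threshold per test. A haemoglobin fall from 140 to 105, or from 125 to 85 g/L, does not reach 80 and is not counted. Clearance worsening that stays at or above 50 mL/min is not counted either, unless creatinine also passes 132.605 µmol/L. Below the threshold any further fall qualifies, for example from 48 to 47 mL/min, so grade changes there are not distinguished.
- *Changes from baseline.* These are distribution summaries by visit, not numbers of patients who worsened.
- *Baseline tables.* SAP 4.2.6.5 grades baseline clearance, but as a marginal count, and its Grade 1 limit is the local lower limit of normal (75 only if that is missing), whereas Table 11 fixes 75. Baseline haemoglobin is summarised but not graded.
- *Adverse events.* The treatment-emergent definition (SAP 4.2.8.3) broadly requires onset or worsening after the start of drug, but it counts reported events, not graded laboratory values.

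No described output sets baseline grade against worst grade for either test.

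**3. Possible size, by simulation with zero drug effect.** Assumptions, none of them from the documents: normally distributed true values; within-patient SD of 4 g/L for haemoglobin and 8 mL/min for clearance; one baseline value and two to four on-treatment values; haemoglobin mean 135-145 with SD 14-16; clearance mean 85-105 with SD 30.

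| | Worst grade ≥1, current rule | Worst grade above baseline grade | Share of the first column no worse than baseline grade |
|---|---|---|---|
| Haemoglobin | 19-48% | 6-13% | 62-79% |
| Clearance | 20-48% | 9-23% | 46-62% |

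With within-patient variation set to zero, the current rule returns exactly the baseline prevalence and the baseline-referenced count is 0%. The 6-13% and 9-23% are noise: the worst of several values is being compared with a single baseline value.

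**The case against.** The strongest reply is that the SAP hides nothing and handles baseline elsewhere. The rule is stated in words, the output is called Worst Laboratory Values, and the grades are nowhere labelled as toxicity or treatment-emergent. The haemoglobin contrast with and without ribavirin does not rest on this table: changes from baseline, treatment-emergent events, events possibly related to ribavirin, and ribavirin dose changes for anaemia are all reported. The table is descriptive, with no test or decision attached. The table shells in SAP Part II are not available here, so they may already show baseline grades.

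Most of this stands. It limits the point to interpretability and lowers its weight. It does not supply a count of patients whose haemoglobin or clearance grade worsened.

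A reader might infer that the SAP dropped the protocol's baseline-referenced shift tables in favour of a baseline-blind table. The text does not support that: the replacement is the PCS table, which is conditioned on baseline, and the worst-grade summary is introduced as an addition.

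A reader might also infer that the flaw is what makes regimen columns non-comparable. Regimen follows genotype and cirrhosis in any case. That confounding affects every regimen comparison in this non-randomised cohort; Protocol 9.9 acknowledges confounding in general, and the table is already stratified by cirrhosis.

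**Conclusion.** The point holds as a limitation of one supplementary safety table. The haemoglobin and clearance grades describe the worst state observed on treatment, not worsening, and milder worsening has no baseline-conditioned patient count in any described output. The SAP uses a patient-level reference for PCS values and for ALT and AST, and gives no reason for treating these two tests differently.

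The number of patients affected cannot be derived. Applying an assumed baseline prevalence to the 650 planned inclusions would not give it: the documents state no prevalence, the two tests are graded separately, and 650 is not the size of the safety population with on-treatment values. The simulated shares show only that the pre-existing part can be large under plausible assumptions.

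Two stronger statements go beyond the documents. A dialysis patient is not necessarily Grade 4; Grade 3 is possible, as the calculation at 17.2 mL/min shows. Dialysis and age of 85 years or over appear as tabulation categories, which shows that such patients were foreseen, not that any were enrolled.

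The change is worth making because it is cheap and serves the tolerability objective. It does not touch the primary endpoint.

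**What to change.** In output twlv_, for haemoglobin and creatinine clearance:

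- cross-tabulate baseline grade by maximum on-treatment grade, using the Table 11 limits for both;
- report the number and percentage of patients whose maximum grade exceeds their baseline grade;
- show patients without a baseline value in a separate row.

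The current worst-grade counts remain as the margin of the table, so nothing is lost. A footnote should say that the worst of several values is compared with one baseline value, so some apparent worsening is expected without any drug effect.

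The cost is a somewhat larger table shell and its programming. Haemoglobin and creatinine are already documented at baseline and on treatment where available (Protocol 9.4.1.1 and 9.4.1.2), so no new data are needed. The table stays descriptive, and differences between regimen columns remain confounded.

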**Table 11 Definition of CTCAE Grades 0-4**

Laboratory data	Grade 0	Grade 1	Grade 2	Grade 3	Grade 4
ALT	$\leq\text{ULN}$	$\text{>ULN} - 3 \times \text{ULN}$	$> 3 - 5 \times \text{ULN}$	$> 5 - 20 \times \text{ULN}$	$> 20 \times \text{ULN}$
AST	$\leq\text{ULN}$	$\text{>ULN} - 3 \times \text{ULN}$	$> 3 - 5 \times \text{ULN}$	$> 5 - 20 \times \text{ULN}$	$> 20 \times \text{ULN}$
Hemoglobin Decreased [g/L]	$\geq 130$	$< 130 - 100$	$< 100 - 80$	$< 80 - 65$	$< 65$
Creatinine Clearance [ $\text{mL}/\text{min}$ ]	$\geq 75$	$< 75 - 60$	$< 60 - 30$	$< 30 - 15$	$< 15$

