### 9.2.1 Target Population

Patients are eligible for observation in this cohort if the following applies:

- Treatment-naïve or -experienced adult male or female patients with confirmed CHC, genotype 1 or 4, receiving combination therapy with the interferon-free ABBVIE REGIMEN ± RBV according to standard of care and in line with local label.
- If RBV is co-administered with the ABBVIE REGIMEN, it has been prescribed in line with the current local label (with special attention to contraception requirements and contraindication during pregnancy)
- Patients must voluntarily sign and date a patient authorization to use and/or disclose his/her pseudonymized health data prior to inclusion into the study
- Patient must not be participating or intending to participate in a concurrent interventional therapeutic trial

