#### **4.2.6.5 CHC related and other laboratory data at baseline**

The laboratory data at baseline are the most recent available data prior to first administration of the ABBVIE REGIMEN (including day 1, see Table 5). All reported clinical laboratory test results will be assigned to one of the time points using the time windows specified in the Table 5.

A summary table will show CHC related laboratory data at baseline, i.e. HCV RNA in IU/mL, HCV RNA in log10 IU/mL, and HCV RNA categorized using 400,000, 800,000, 6,000,000 and 10,000,000 as cut-offs, ALT, ALT ratio, AST, AST ratio, APRI, FIB-4. ALT-ratio, AST ratio, APRI and FIB-4 will be calculated as follows:

ALT ratio = ALT value / upper limit of normal (ULN) of local laboratory

AST ratio = AST value / ULN of local laboratory

APRI =  $100 \times \text{AST [IU/L]} / (\text{ULN of AST [IU/L]} \times \text{Platelets [10}^{12}/\text{L]})$  (APRI= aspartate aminotransferase to platelet ratio index [1]; calculated, if laboratory assessments took place within 30 days)

FIB-4 =  $(\text{Age [years]} \times \text{AST [IU/L]}) / (\text{Platelets [10}^{12}/\text{L]} \times \text{Square root of ALT [IU/L]})$  (FIB-4= Fibrosis 4 index [2]; calculated, if laboratory assessments took place within 30 days )

In addition the following other key laboratory data at baseline will be summarized: γ-GT, total bilirubin, albumin, creatinine, creatinine clearance (continuous and categorize as Grade 1 [60-<LLN mL/min], Grade 2 [30-<60 mL/min], Grade 3 [15-<30 mL/min], Grade 4 [<15 mL/min]; if LLN is missing 75 mL/min is used), AFP, hemoglobin, platelets, prothrombin time, and INR (if documented instead of prothrombin time). The creatinine clearance will be calculated as follows:

Creatinine clearance [ml/min] =  $(140-\text{age}) \times \text{Weight (in kg)} \times \text{constant/Creatinine (in } \mu\text{mol/L)}$   
(constant is 1.23 for men and 1.04 for women; calculated by Cockcroft-Gault-Formula)

A further table CD4 and HIV-RNA test results are displayed for patients with HIV only.

**Table 7** Overview of Outputs for Baseline Characteristics

Output Title	Output Short Name	Analysis Population
Socio-demographic Characteristics by Genotype and Cirrhosis Status - CP - <country>	tdm_<c>_gc_cp	Core population
Socio-demographic Characteristics by Genotype and Cirrhosis Status - TP - <country>	tdm_<c>_gc_tp	Target population

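### SAP Table 11 uses one 130 g/L haemoglobin limit for both sexes, so women between their own lower limit of normal and 130 g/L are tabulated as Grade 1 decreased haemoglobin (minor)

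*SAP*

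**What the plan says.** The haemoglobin row of SAP Table 11, "Hemoglobin Decreased [g/L", has fixed limits: Grade 0 at 130 or more, Grade 1 from 100 to below 130, Grade 2 from 80 to below 100, Grade 3 from 65 to below 80, Grade 4 below 65. It has no entry by sex, no reference to a laboratory LLN and no footnote.

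The text under Table 10 in SAP 4.2.8.4 plans to summarise, "for hemoglobin and creatinine clearance, the number and percentage of subjects with a maximum Common Terminology Criteria for Adverse Events (CTCAE) Grade", taken "at any post-baseline visit (regardless of the baseline value) through the end of treatment". On the layout of the laboratory analyses, SAP 4.2.8.4 says: "All will be performed for the SP by treatment regimen and cirrhosis status". Sex is not a stratum. Protocol 9.2.1 admits "adult male or female patients with confirmed CHC".

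Three other places bear on the point:

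- Protocol 9.7.4 planned laboratory values "categorized as low, normal, or high based on reference ranges used in this study". SAP 4.2.8.4 replaces the resulting shift tables with criteria for potentially clinically significant (PCS) values, and says so: "Instead of the shift tables mentioned in the study protocol".
- In Table 11 itself, ALT and AST have their Grade 0/1 boundary at the ULN, while creatinine clearance has a fixed 75 mL/min.
- At baseline (SAP 4.2.6.5), creatinine clearance is graded against the LLN, "Grade 1 [60-<LLN mL/min", with 75 mL/min only where the LLN is missing.

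**The concern.** If the lower limit of normal for women is below 130 g/L, a fixed 130 g/L puts some women with in-range values into a row labelled as decreased haemoglobin. They need not have had any fall: a woman at 126 g/L before and throughout treatment, against an assumed limit of 120 g/L, is counted as Grade 1.

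Haemoglobin is a laboratory value that readers of these tables will look at. The protocol's background section mentions ribavirin-induced haemolysis, the safety groups contrast regimens with and without ribavirin, and anaemia is a listed reason for changing or stopping ribavirin. The PCS criterion starts only below 80 g/L and the shift tables are gone, so the grade table is the planned categorical display of mild and moderate decreases. A Grade 1 row that mixes women with in-range values and patients with low values is harder to interpret.

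**Working it through.** There is no stated figure to reproduce here. The check applies Table 11 as written and then sizes the affected band.

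**Step 1: the rule as written.** 130 g/L gives Grade 0. Values of 129, 125, 120 and 115 g/L all give Grade 1, for men and women alike. 99 gives Grade 2, 79 Grade 3, 64 Grade 4. With a female LLN of L below 130, women whose lowest value lies from L to below 130 g/L are Grade 1 although every value is in range. If L is 130 or higher, nobody is affected.

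**Step 2: inputs.** All of these are assumptions, because neither document gives a haemoglobin range, mean or SD: L = 115, 120 or 125 g/L; mean m = 132, 135 or 138 g/L in women; between-person variance 75 and within-person SD 5, so total SD = √(75 + 25) = 10; no drug effect. The number k of on-treatment values is taken as 2 or 3. The planned contacts suggest this: an early on-treatment visit and end of treatment, plus a mid-treatment visit for 24-week patients (protocol 9.1, Table 2 and Annexes 5 and 6). Routine practice may produce other numbers.

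**Step 3: one value, L = 120.** Share = Φ((130 − m)/10) − Φ((120 − m)/10).

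- m = 132: 0.421 − 0.115 = 0.306
- m = 135: 0.309 − 0.067 = 0.242
- m = 138: 0.212 − 0.036 = 0.176

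Over a wider grid for one value (L 115 to 125, mean 130 to 140, SD 8 to 12), the share runs from about 8% to 47% of women.

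**Step 4: worst of k values.** For a woman with true level u, all k values are at or above c with probability [1 − Φ((c − u)/5)]^k. Averaging over u ~ N(m, 75) gives P(min ≥ c). The share in the band is P(min ≥ L) − P(min ≥ 130).

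| Assumed female LLN (g/L) | k = 2; m = 132 / 135 / 138 | k = 3; m = 132 / 135 / 138 |
|---|---|---|
| 115 | 46 / 37 / 28% | 50 / 42 / 32% |
| 120 | 36 / 31 / 24% | 39 / 34 / 27% |
| 125 | 20 / 18 / 15% | 21 / 20 / 17% |

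The overall range is about 15% to 50% of women, and 24% to 39% at L = 120.

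**Step 5: effect on a regimen comparison.** The contribution to a difference in Grade 1 between two groups is (difference in proportion of women) × (share in band). The documents do not give the sex mix by regimen. As an illustration, a 10-point difference with the 34% share gives 0.10 × 34 = 3.4 percentage points. With equal proportions of women the contribution from sex mix is zero.

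**The case against.** The strongest reply is that this is one boundary, the mildest, in an untested descriptive table, and that haemoglobin is not treated as a special case. That is largely right. Table 11 also gives creatinine clearance a fixed limit, so both parameters graded for a decrease use fixed values on treatment; the LLN rule belongs to the separate baseline table. The protocol's reference-range wording does not promise local or sex-specific ranges, and the SAP replaces the shift tables openly.

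The reply also holds on data. Protocol 9.4.1.1 to 9.4.1.3 list the ULN for ALT and AST but no LLN for haemoglobin, and 9.6.1 restricts eCRF entry to data specified in the protocol. A rule built on the local LLN might have nothing to work with.

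A reader might go on to infer that ribavirin comparisons are confounded by sex, or that a ribavirin effect is diluted. The documents do not establish either. Regimen is tied to genotype and cirrhosis in the core-population rules, and nothing is said about sex by regimen. A reader might also infer that all women with normal haemoglobin are misgraded; those at or above 130 g/L are Grade 0. Ribavirin-related changes remain visible in mean changes from baseline, Grades 2 to 4, the PCS table, the adverse-event tables and ribavirin modifications for anaemia.

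What the reply does not remove is the plain effect of the rule: for any female limit below 130 g/L, some in-range women are labelled as having decreased haemoglobin. Disregard of baseline is a separate matter that affects both sexes.

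**Conclusion.** The point holds, as a minor one. As written, Table 11 counts women between their own LLN and 130 g/L as Grade 1. Under the stated assumptions this is about 15% to 50% of women for the worst of two or three values, and 24% to 39% if the female limit is 120 g/L. The direction depends only on the female limit being below 130 g/L; the size depends on that limit, the haemoglobin distribution and the number of measurements, none of which the documents supply. Whether any comparison between regimens is distorted cannot be judged from the documents. The primary endpoint is not involved.

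**What to change.** In Table 11, set the haemoglobin Grade 0/1 boundary by sex with limits fixed in advance: for example, keep 130 g/L for men and use a stated lower value such as 120 g/L for women, identified as the sponsor's chosen reference. Use a local LLN instead only where one was actually captured. Leave Grades 2 to 4 unchanged.

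The cost is one table row and one derivation; sex is already collected. There are two small downsides. The female limit is a convention that has to be justified, and Grade 1 counts will no longer compare directly with studies that used the single limit.
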